6.0 Study Design

Each participant will be followed with a study visit in the Clinic on Day 1, and subsequent decentralized, remote study visits on Days 29, 57, and 85. The total duration of study participation is planned to be 85 ± 3 days.

On Day 1, each participant will be randomized 2:1 to either Cohort A or Cohort B. Tasso+™ blood samples of participants randomized to Cohort A will be shipped to the Central Laboratory where they will be centrifuged and aliquoted. However, Tasso+™ blood samples of participants randomized to Cohort B will be centrifuged and aliquoted at the Site prior to shipping to the Central Laboratory, following the same approach used for venipuncture blood samples.

The decentralized visit on Day 29 (Visit 2) will be remotely supported by a prescheduled proctor during working hours to support the participant's self-administration of the Tasso+™ device. For the decentralized visit on Day 57 (Visit 3), the participant will have the option to request a prescheduled proctor session during working hours to support the participant's self-administration of the Tasso+™ device. The participant will use an electronic diary (eDiary) to report symptoms for 28 days following each Tasso+™ device administration (Symptom questionnaire) and to report on the usability of the Tasso+™ device (Tasso questionnaire) immediately following each Tasso+™ device administration (on Days 1, 29, and 57) and on Day 85. Contact information will be provided to each participant in the event they have concerns or they need help during working hours while using the Tasso+™ device.

Statistical Analysis Plan (SAP)

Protocol: Phase 1 Study Evaluating Technologies for Point-of-Care Blood Collections in Support of Decentralized Outpatient Assessments in Pandemic and Clinical Trial Settings

Version Date: 27-Jun-2025

Sponsor: Resilience Government Services, Inc.

Protocol No: 5309/0024

Venous blood collection (phlebotomy) will take place on Day 1; capillary blood collections using Tasso+™ device will take place on Days 1, 29, and 57; usability data will be collected after each use of Tasso+™ device and on Day 85; reliability of the device will be collected after each use of Tasso+™ device (Days 1, 29, and 57). Each Tasso+™ capillary blood collection will be followed by a 28-day follow-up period during which safety of the Tasso+™ device will be assessed using an eDiary (Symptom questionnaire).

Each self-collected Tasso+™ blood sample will be assessed for sample integrity by the Central Laboratory. Moreover, on Day 1, the self-collected capillary blood sample will be compared to a venous blood sample collected by an HCP, in order to assess device performance.

Each participant will receive nasopharyngeal swabbing on Day 1 for SARS-CoV-2 PCR testing to identify any baseline SARS-CoV-2 infections. The nasopharyngeal swab will be performed and resulted by the Site. These participants may remain on study but will be referred to their primary physician for COVID-19 management. During the study, if participants experience any COVID-19 symptoms or if they became COVID-19 positive, they are to be reported to the Investigator. SARS-CoV-2 antibody testing (Days 1 and 57) will be conducted to serologically identify intervening COVID-19 cases, or if in the absence of intervening symptoms, SARS-CoV-2 infections.

The Study Schematic and Schedule of Assessments are available in [Figure 1](#) and [Table 1](#) respectively.

Figure 1: Study Schematic

[figure not shown]
Statistical Analysis Plan (SAP)

Protocol: Phase 1 Study Evaluating Technologies for Point-of-Care Blood Collections in Support of Decentralized Outpatient Assessments in Pandemic and Clinical Trial Settings

Version Date: 27-Jun-2025

Sponsor: Resilience Government Services, Inc.

Protocol No: 5309/0024

Footnotes:

- a eDiary will be completed during each follow-up period to collect safety data (Symptom questionnaire) and user experience (Tasso questionnaire).
- b Day 1 collection to be site-supervised; venipuncture samples (SST and EDTA tubes) and Cohort B Tasso+™ samples (SST and EDTA capillary collection tubes) to be centrifuged and aliquoted by the Site before shipping; venipuncture samples (SST and EDTA tubes) and Tasso+™ samples (SST and EDTA capillary collection tubes) to be shipped to Central Laboratory by the Site; Cohort A Tasso+™ samples (SST and EDTA capillary collection tubes) to be centrifuged and aliquoted by the Central Laboratory upon receipt.
- c Day 29 collection to be remotely proctor-supported (during working hours); Tasso+™ samples (SST and EDTA capillary collection tubes) to be packaged and shipped to Central Laboratory by the participant.
- d Day 57 collection to be remotely proctor-supported (during working hours), as requested; Tasso+™ samples (SST and EDTA capillary collection tubes) to be packaged and shipped to Central Laboratory by the participant.
- e eDiary (Tasso questionnaire) will be completed immediately following each Tasso+™ administration and on Day 85 to document the user experience.

Statistical Analysis Plan (SAP)

Protocol: Phase 1 Study Evaluating Technologies for Point-of-Care Blood Collections in Support of Decentralized Outpatient Assessments in Pandemic and Clinical Trial Settings

Version Date: 27-Jun-2025

Sponsor: Resilience Government Services, Inc.

Protocol No: 5309/0024

Table 1 Schedule of Assessments

Assessments	Visits ^a			
	Visit 1	Visit 2	Visit 3	Visit 4
Study Day (±visit window)	1	29±3	57±3	85±3
In-clinic	X			
Decentralized (eg, home) ^b		X	X	X
Proctor session ^c		X ^c	(X) ^c	
Training	X ^c	X ^c	(X) ^c	
Informed consent (eConsent)	X			
Demographics	X			
Medical history ^d	X			
Concomitant medication	X	X	X	X
Vital signs ^e	X			
Physical examination ^f	X			
Pregnancy urine test (females only)	X			
Eligibility check	X			
Randomization (IVRS)	X			
COVID-19 symptom screen ^g	X	X	X	X
Nasopharyngeal swab for SARS-CoV-2 PCR ^h	X			
Tasso+™ collection				
SST capillary collection tube (left upper arm preferred)	X ^{il}	X ^{jl}	X ^{kl}	
EDTA capillary collection tube (right upper arm preferred)	X ^{il}	X ^{jl}	X ^{kl}	
Venous blood collection				
SST tube	X ^{im}			
EDTA tube	X ^{im}			

Statistical Analysis Plan (SAP)

Protocol: Phase 1 Study Evaluating Technologies for Point-of-Care Blood Collections in Support of Decentralized Outpatient Assessments in Pandemic and Clinical Trial Settings

Version Date: 27-Jun-2025

Sponsor: Resilience Government Services, Inc.

Protocol No: 5309/0024

Assessments	Visits ^a			
	Visit 1	Visit 2	Visit 3	Visit 4
Study Day (±visit window)	1	29±3	57±3	85±3
eDiary				
Tasso questionnaire (user experience)	X	X	X	X
Symptom questionnaire (AEs/SAEs) ⁿ	X	X	X	X

AE=adverse event; EDTA=ethylenediaminetetraacetic acid; IFU=instruction for use; IVRS=interactive voice response system; HCP=healthcare professional; PCR=polymerase chain reaction; SAE=serious adverse event; SST=serum-separator tube

Footnotes:

- a If a participant withdraws from the study early, the assessments planned for the last follow-up/end of study Visit should be completed at the time of withdrawal.
- b Defined as any remote location of convenience for the participant where the administration can be done with appropriate technique in a clean environment where samples can be packaged for shipment.
- c When administering the Tasso+™ remotely, participants will receive proctor-support on Day 29 (and as requested, on Day 57), the intent being to guide the participant through the process and to help troubleshoot should any difficulties be encountered. Proctor sessions will be prescheduled by the Site to take place during working hours. Training will be performed on Day 1 (by Site) and Day 29 (by Proctor). Training on Day 57 should be performed only if requested by the participant. Training may include detailed IFU and online video training (see [Section 7.4](#) and IFU provided separately). While assistance will be available to the participant during Day 57 Visit, it is of interest to know whether the prior trainings on Tasso+™ administration prove adequate for this subsequent administration.
- d Includes COVID-19 illness/vaccine history details (if available).
- e Vital signs include heart rate, systolic and diastolic blood pressure, respiratory rate, SpO2 by pulse oximetry, and body temperature (taken by ear/tympanic/temporal, oral, or forehead method). The assessment of heart rate and blood pressure will be conducted in the supine position after a minimum rest period of 5 minutes.
- f Physical examination includes general appearance, skin, eyes, ears, nose, throat, head and neck, heart, chest and lungs, abdomen, extremities, lymph nodes, musculoskeletal, neurological, and other body systems, if applicable, for describing the status of the participant's health.
- g The development of any COVID-19 symptoms should prompt the participant to contact the Investigator via provided Site's phone number.
- h Nasopharyngeal swab for SARS-CoV-2 PCR will be performed and resulted by the Site.
- i Day 1 collections: venipuncture samples by HCP (SST and EDTA tubes) and Tasso+™ samples by participant (SST and EDTA capillary collection tubes; Cohort B only) to be centrifuged and aliquoted by the Site before shipping; venipuncture samples by HCP (SST and EDTA tubes) and Tasso+™ samples by participant (SST and EDTA capillary collection tubes) and to be shipped to Central Laboratory by the Site.
- j Day 29 collection remotely proctor-supported (during working hours); Tasso+™ samples (SST and EDTA capillary collection tubes) to be packaged and shipped to Central Laboratory by the participant.
- k Day 57 collection remotely proctor-supported, as requested (during working hours); Tasso+™ samples (SST and EDTA capillary collection tubes) to be packaged and shipped to Central Laboratory by the participant.
- L Tasso+™ samples will be tested by Central Laboratory. Assessments include (by order of priority):
 - Volume measurement (SST and EDTA capillary collection tubes), hemolysis (SST and EDTA capillary collection tubes), and evidence of clotting (EDTA capillary collection tube only).
 - Chemistry analytes (SST capillary collection tube): sodium, potassium, chloride, blood urea nitrogen, creatinine, glucose, phosphate, uric acid, and C-reactive protein.
 - Serology (SST and EDTA capillary collection tubes); any participant who is positive for IgG Nucleocapsid assay for either capillary matrix (SST or EDTA) will be considered positive.
- m Venipuncture samples will be tested by Central Laboratory. Assessments include:
 - Chemistry analytes (SST tube): sodium, potassium, chloride, blood urea nitrogen, creatinine, glucose, phosphate, uric acid, and C-reactive protein.
 - Serology (SST and EDTA tubes); any participant who is positive for IgG Nucleocapsid assay for either matrix (SST or EDTA) will be considered positive.
- n Including training for eDiary on Visit 1. Participant can report any AE in the eDiary (Symptom questionnaire). Safety data collection will be solicited from participant for the first 7 days after Tasso+™ device administration, and unsolicited AEs will be captured for the full 28-day period after each administration.

Statistical Analysis Plan (SAP)

Protocol: Phase 1 Study Evaluating Technologies for Point-of-Care Blood Collections in Support of Decentralized Outpatient Assessments in Pandemic and Clinical Trial Settings

Version Date: 27-Jun-2025

Sponsor: Resilience Government Services, Inc.

Protocol No: 5309/0024

6.1 Sample Size Considerations

Sample size was not calculated on a formal statistical basis; however, the sample size of 200 is large enough to illustrate diversity of user experience regarding the unsupported use of Tasso+™ for capillary blood collection.

6.2 Randomization

Each participant will have a unique subject screening number obtained from the interactive voice response system (IVRS). Once the participant is deemed eligible, the participant will be assigned a randomization number.

Randomization will be performed via a centralized IVRS. On Day 1, eligible participants will be assigned to either Cohort A or Cohort B in a 2:1 ratio. Thus, it is planned to randomize approximately 133 participants into Cohort A and approximately 67 participants into Cohort B.

6.3 Analysis Population Sets

Three analysis sets will be used: the Full Analysis Set (FAS), Per-Protocol Set (PPS), and Safety Analysis Set (SAS).

6.3.1 Full Analysis Set (FAS)

The FAS is defined as all participants who administered Tasso+™ either in a site-supervised, proctor-supported, or unsupported setting. This analysis set will be the primary set used for analyses/summaries of the primary endpoint, as well as for secondary endpoints of seroconversion.

6.3.2 Per-Protocol Set (PPS)

The PPS will include all participants who successfully completed at least five Tasso+™ administrations and do not have any important protocol deviations. This analysis set will be used for sensitivity analyses.

If the FAS and PPS include the same set of participants, only one set of analyses will be produced.

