9.4.2 Secondary Endpoints

9.4.2.1 Safety

Counts and percentages will be presented for participants in the FAS who experience:

- Solicited local AEs (including pain, tenderness, redness, swelling, or bruising)

- Unsolicited AEs
- A related Grade 3 AE
- A related Grade 4 AE
- A related AE leading to discontinuation
- A related SAE

9.4.2.2 *Tolerability*

The counts and percentages of participants in the FAS who complete the Day 57 Visit will be summarized.

9.4.2.3 *Usability*

Descriptive statistics will be presented for participants in the FAS for each aspect of the usability questionnaire on Days 1, 29, 57, and 85.

9.4.2.4 *SARS-CoV-2 Infection Surveillance*

Counts and percentages will be presented for participants in the FAS for:

- Participants with a positive nasopharyngeal swab for SARS-CoV-2 PCR on Day 1
- Participants seroconverting to SARS-CoV-2 between Days 1 and 57

9.4.3 *Exploratory Endpoint*

Descriptive statistics will be presented for participants who requested proctor support on Day 57 Visit and for participants who completed the Day 57 Visit without using the proctor support, for the following primary and secondary endpoints:

- Sample integrity
- Reliability
- Safety
- Usability

9.4.4 *Analysis of Safety*

The SAS will be used for the analysis of safety data.

AEs will be coded with MedDRA. AEs are defined as events with an onset date on or after the date of first administration of the medical device and before the date of last administration of the medical device (Visit 3, Day 57 ± 3) +28 days, which corresponds to the Visit 4 (Day 85 ± 3). TEAEs will be presented by system organ class and preferred term in frequency tables. Participants with multiple AEs will be counted only once within each preferred term and system organ class.

Laboratory data (sodium, potassium, chloride, blood urea nitrogen, creatinine, glucose, phosphate, uric acid, and C-reactive protein) will be converted to Système International units for reporting and processing purposes. Absolute values will be presented descriptively. Laboratory data outside study-specific reference ranges will be listed.

9.4.5 *Demographic and Baseline Characteristics*

Demographic characteristics (including age, sex, ethnicity, and race) and baseline characteristics (including height, weight, BMI, supine systolic and diastolic blood pressure, pulse, body temperature, and respiratory rate) will be presented descriptively.

Prior and concomitant medications will be listed.

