9.5.3.2 Tolerability

The count and percentage of participants in the FAS who completed their Day 57 Tasso+™ administration will be summarized, where completion is defined as having completed at least one of Tasso+™/SST or Tasso+™/EDTA at the visit.

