9.5.4 Exploratory Endpoints

9.5.4.1 Proctor Support

Descriptive statistics will be presented for participants who requested proctor support on the Day 57 Visit and for participants who completed the Day 57 Visit without using the proctor support in the PPS, for the following primary and secondary endpoints:

- Sample integrity
- Reliability
- Safety
- Usability

Statistical Analysis Plan (SAP)

Protocol: Phase 1 Study Evaluating Technologies for Point-of-Care Blood Collections in Support of Decentralized Outpatient Assessments in Pandemic and Clinical Trial Settings

Version Date: 27-Jun-2025

Sponsor: Resilience Government Services, Inc.

Protocol No: 5309/0024

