9.5.4.2 Sample Integrity

A sample integrity sub-group analysis will be conducted among only the samples collected on or after December 10th, 2024, the date at which updated sample collection instructions were implemented. The same sample integrity criteria used for the primary endpoint (volume, hemolysis, and clotting) will be summarized using frequencies and percentages by time point, collection method, and cohort.

This sub-group analysis will be conducted in the PPS.

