9.5.4.3 Testing Accuracy

A stratified testing accuracy analysis will be conducted using the following two strata:

- Samples received by the central laboratory \leq 1 day after collection (ie, received by the central laboratory either on the same day as collection or the day following collection)
- Samples received by the central laboratory $>$ 1 day after collection

Contingency correlation coefficient will be computed to estimate the extent of the relationship between the venipuncture collection and the Tasso+™ collection at Day 1 by cohort for each biochemistry parameter.

This stratified analysis will be conducted in the PPS.

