9.5.4.4 Percentage of Subjects with Complete Analyte Profile

The frequency and percentage of subjects who met the following criteria will be summarized by time point in the PPS:

- Had all of their biochemistry analytes resulted at the given time point (for SST)
- Had their SARS-CoV-2-IgG sample resulted (for SST)
- Had all of their biochemistry analytes and SARS-CoV-2-IgG sample resulted (for SST)
- Had their SARS-CoV-2-IgG sample resulted (for EDTA)

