9.5.4.5 Summary of Collected Sample Volume

Boxplots will be produced to visualize the volume of sample collected for each subject by time point and collection method (SST or EDTA). The x-axis of the boxplot will be split by cohort (for Day 1 only), with two boxplots for each cohort (one for SST and one for EDTA). Day 29 and Day 57 boxplots will summarize all subjects combined, with one boxplot for SST and one boxplot for EDTA. The figure will be produced for the PPS.

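### Day 57 reliability by proctor support (SAP 9.5.4.1) and complete analyte profiles (SAP 9.5.4.4) are planned only in a per-protocol set that requires five successful administrations, so failure can be understated

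*SAP*

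**What the plan says.** Participants make two collections, one SST and one EDTA, on each of Days 1, 29 and 57 (protocol 6.2).

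- **PPS entry rule, SAP 6.3.2:** "The PPS will include all participants who successfully completed at least five Tasso+™ administrations and do not have any important protocol deviations". The same section gives the set's purpose as sensitivity analyses. Protocol 9.2 is stricter and requires success at all administrations. Neither current text defines success.
- **SAP 9.5.4.1:** Day 57 sample integrity, reliability, safety and usability are summarized for those who requested support and for "participants who completed the Day 57 Visit without using the proctor support in the PPS". The words on the PPS could be read as applying to the second group only. The two groups would then come from different analysis sets, which is no better.
- **SAP 9.5.4.4:** "The frequency and percentage of subjects who met the following criteria will be summarized by time point in the PPS".
- **Protocol 9.4.3:** the matching sentence reads "participants who completed the Day 57 Visit without using the proctor support, for the following primary and secondary endpoints", with no analysis set named. The PPS restriction enters with the SAP.
- **FAS:** everyone who administered the device in any setting (SAP 6.3.1), whatever the result.
- **Repeat kits:** one may be supplied after a collection failure (protocol 4.3 and 6.3.3). Whether a good repeat counts towards the five is not stated.

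**The concern.** Success is the ticket of entry to two summaries of success. SAP 9.5.4.1 is the only planned analysis of the exploratory objective, which asks whether earlier training is adequate for Day 57 home collection. The participants most informative about inadequate training are those who fail on Day 57, and they are the ones most likely to be left out.

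For SAP 9.5.4.4, part of what makes a profile incomplete is a failed collection, and repeated failures remove the participant from the table. A participant who stops before Day 57 has at most four scheduled administrations. Extra kits aside, that participant also leaves the Day 1 and Day 29 percentages.

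A sensitivity set is meant to be read beside a main analysis. For these two outputs there is no main analysis.

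**Working it through.** The plan has no formal sample size (SAP 6.1) and no hypothesis test (SAP 9.5.1), so there is no planning figure to reproduce.

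**Step 1: count.** 2 tubes × 3 visits = 6 scheduled administrations. Suppose a failed collection is not successful and only scheduled tubes count. Then at least 5 of 6 means at most 1 unsuccessful, a ceiling of 1/6 = 16.7% of scheduled administrations. Two failed Day 57 tubes leave at most 4 successes, so that participant is excluded.

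**Step 2: inputs for an illustration.** Protocol 1.2 cites one earlier study in which 70.0% of participants obtained an adequate sample and another with 93.4% success unsupervised. Their complements, 30% and 6.6%, are used as assumed failure rates per use, p. They are participant-level rates of inadequate or unsuccessful samples, not the reliability failures of protocol 6.3.3. Failures are taken as independent, and exclusions for protocol deviations are not modelled.

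**Step 3: no repeat kits.**

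P(in PPS) = (1−p)^6 + 6p(1−p)^5

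Failure rate in the PPS = p(1−p)^5 / P(in PPS) = p/(1+5p)

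- p = 0.30: P(in PPS) = 0.1176 + 0.3025 = 0.420; failure 0.30/2.5 = 12.0%.
- p = 0.066: P(in PPS) = 0.945; failure 0.066/1.33 = 5.0%.

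**Step 4: every failure repeated once, good repeats count.** An administration is then unsuccessful with probability f = p². Inside the PPS that share is g = f/(1+5f). Among successful administrations, the share that needed a repeat is r = p/(1+p).

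Failure per use in the PPS = [2g + (1−g)r] / [2g + (1−g)(1+r)]

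- p = 0.30: f = 0.09, g = 0.0621, r = 0.2308; 0.3406/1.2785 = 26.6%.
- p = 0.066: f = 0.00436, g = 0.00426, r = 0.0619; 0.0702/1.0659 = 6.6%.

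| Assumed failure per use, all participants | In PPS, no repeats | In PPS, all repeated | Retained in PPS (no repeats / all repeated) |
|---|---|---|---|
| 30% | 12.0% | 26.6% | 42.0% / 90.5% |
| 6.6% | 5.0% | 6.6% | 94.5% / 99.97% |

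**Step 5: very low rates.** Protocol 1.1.3 reports customer feedback on more than 40,000 third-generation devices. The categories that match protocol 6.3.3 are no blood (8), lancet (4), damage (1) and adhesive (1), so 14/40,000 = 0.035%. Then 0.00035/1.00175 is still 0.035%.

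**Step 6: failures clustered within participants.** With an assumed beta-binomial correlation of 0.1 to 0.3 and no repeats, 30% appears as 9.8% to 6.5%, and 6.6% as 3.5% to 1.9%. The documents give no value for this correlation.

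**Step 7: complete profiles, SST collection component.** Without repeats, 1−p against 1−p/(1+5p): 70.0% becomes 88.0% and 93.4% becomes 95.0%. With all failures repeated, 1−f against 1−g: 91.0% becomes 93.8%, and 99.6% stays 99.6%. These are ceilings on the SAP 9.5.4.4 percentage. Each must be multiplied by the unknown share of collected SST samples with every analyte resulted.

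**Step 8: Day 57 contrast, all inputs assumed.** Take Day 57 failure of 30% in one group and 15% in the other, with 15% at the four earlier administrations. Without repeats, the PPS rates are 16.7% and 8.6%, so a 15-point gap shows as 8.1 points. With all failures repeated it shows as 13.8. The shrinkage is the same whichever group does worse.

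**The case against.** **The certainty depends on an undefined term.** A reader might infer that no participant without a Day 57 sample can appear in either support group, and that Day 57 completion in the PPS is 100% by construction. SAP 9.5.3.2 says "completion is defined as having completed at least one of Tasso+™/SST or Tasso+™/EDTA at the visit", which makes that reading tempting. The documents do not support it without conditions. If *successfully completed* meant only that the procedure was carried out, a use yielding no blood could qualify. If extra kits add to the count, five can be reached without a Day 57 success. This objection stands, and the exclusion is conditional.

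**Existing tables show some of the effect.** SAP 9.1 lists exclusions with reasons, SAP 9.4 summarizes PPS exclusions by cohort and overall, and SAP 9.3.1 tabulates device use with and without a proctor. Day 57 integrity and overall reliability run in both FAS and PPS (SAP 9.5.2.1, 9.5.2.3), and Day 57 completion runs in the FAS. All true, but none gives Day 57 reliability by support, or complete profiles, in the FAS.

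**The group definitions are uneven already.** Protocol 9.4.3 sets those who requested support against those who completed the visit without it. Changing the analysis set alone would not cure that. Classifying by support actually used fits the endpoint in protocol 3.3, which compares supported with unsupported administrations.

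**The other exploratory outputs are different.** A reader might infer that all five parts of SAP 9.5.4 understate failure, since 9.5.4.2 ("This sub-group analysis will be conducted in the PPS"), 9.5.4.3 ("This stratified analysis will be conducted in the PPS") and 9.5.4.5 ("The figure will be produced for the PPS") also name only the PPS. The documents do not show that. 9.5.4.2 and 9.5.4.5 describe samples collected, so any effect turns on how success relates to volume, hemolysis and clotting. For 9.5.4.3, a correlation, the issue is lost pairs.

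**The effect may be trivial.** At 6.6% with repeats counted, it is. This stands.

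**Conclusion.** The point holds for reliability in SAP 9.5.4.1 and for SAP 9.5.4.4. Both are run only in a set whose entry depends on the outcome described, and the SAP itself assigns that set to sensitivity analyses. Provided a failed collection is not a success and only scheduled tubes count, failure can be understated and completeness overstated.

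The size runs from nothing visible at very low failure rates, or at 6.6% with counted repeats, to a large distortion at 30% with no repeats. The large figures rest on borrowed rates and assumed independence or clustering. The direction of any supported-versus-unsupported difference cannot be predicted, because participants choose whether to ask for Day 57 support.

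It would be wrong to conclude that the study's main results are compromised. The primary endpoints are reported in the FAS, and the affected outputs are exploratory and descriptive. The change should still be made: until success and repeat kits are defined, a reader of these two tables cannot tell how much failure was selected out.

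**What to change.** 1. Present SAP 9.5.4.1 and 9.5.4.4 in the FAS, with the PPS as sensitivity.
2. In 9.5.4.1, classify everyone who attempted Day 57 collection by the proctor support actually used, whether or not the visit was completed. Use device uses as the denominator for reliability.
3. In 9.5.4.4, use as denominator all FAS participants who attempted collection at that time point.
4. Define *successfully completed*, state whether repeat kits count towards the five, and reconcile SAP 6.3.2 with protocol 9.2.
5. Optional: add FAS versions of 9.5.4.2, 9.5.4.3 and 9.5.4.5, so that valid samples are not dropped because of failures at other visits.

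The FAS and PPS runs of the primary endpoints stay as planned. The cost is SAP wording and a few extra tables, with no new data. The exploratory figures may look less favourable.
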